4.2.1. Reasons for Withdrawal/Discontinuation

Discontinuation of study treatment does not represent withdrawal from the study.

Patients may voluntarily withdraw from the study at any time and for any reason without prejudice to their future medical care by the investigator or at the study site. The investigator may withdraw a patient if it is in the best interest of the patient. The Sponsor also reserves the right to discontinue the study at any time for either clinical, administrative, or business reasons, and to discontinue participation by an individual investigator or site for poor enrollment or noncompliance.

Patients may be removed from study treatment, from on-treatment study assessments, or from off-treatment study assessments but continue to be monitored in the study for the following reasons:

- Recurrent Grade 2 pneumonitis

- Patient was erroneously admitted into the study or does not meet entry criteria
- Patient experiences a serious or intolerable AE or clinically significant laboratory abnormality that, in the opinion of the investigator, would affect the ability of the patient to continue on the clinical study
- Patient has progressive disease
- Patient voluntarily decides to withdraw
- Patient is lost to follow-up
- Patient requires treatment with any prohibited medication outlined in the exclusion criteria and/or [Section 5.6](#) other than the use of appropriate medications for the treatment of AEs under the direction of the investigator
- Patient is noncompliant with the study procedures and scheduled assessments
- Patient develops an intercurrent disease or medical condition that, in the opinion of the investigator, would affect the ability of the patient to continue on the clinical study.

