- In the next 6 patients (patients 7 to 12), if again, 2 or fewer of these patients have DLTs observed, enrollment can continue. If DLTs are observed in more than 2 of patients 7 to 12, the time interval between galinpepimut-S doses for the inoculation following the one associated with the DLT will be doubled, , but pembrolizumab will continue as scheduled.
- If DLTs are observed in more than 2 patients of the first 6 (patients 1 to 6) and again in more than 2 patients of the next 6 (patients 7 to 12), the time interval between galinpepimut-S doses will be doubled for two (2) inoculations following the one associated with the DLT. For example, if galinpepimut-S was given on a Q3W schedule before the DLT occurred, it should be given Q6W for the 2 immediately subsequent administrations after the dosing event associated with the DLT, while keeping the pembrolizumab dose and frequency stable.

- If DLTs continue to be observed above 2 per every 6 patients beyond these first 12 patients, and even after the changes in administration of galinpepimut-S, the study will be stopped and the safety data will be examined by the sponsor in consultation with investigators in order to determine how to proceed or whether to discontinue the study.
- Should a given patient experience any of the above DLTs at any time after the completion of the first cycle of co-administration of galinpepimut-S in combination with pembrolizumab, the time interval between galinpepimut-S doses for the inoculation following the one associated with the DLT will be doubled, but pembrolizumab will continue as scheduled.
- If another DLT occurs in that next cycle, the time interval between galinpepimut-S doses will be doubled for two (2) inoculations following the one associated with the DLT, but pembrolizumab will continue as scheduled.
- If no DLTs re-occur after the above periods of doubly 'spaced out' administrations, then the patient should revert back to the initial GPS Q3W schedule (as per the initial dosing frequency/ investigational agent administration schedule).
- If a DLT occurs after these dose modifications in subsequent cycles, the patient will be discontinued from the study.

The above dose density modifications in response to DLTs is further summarized in the bulleted list of actions below:

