- i. The serum chemistry assessments will include sodium, potassium, chloride, carbon dioxide, blood urea nitrogen, creatinine, calcium, total protein, albumin, glucose, total bilirubin, alkaline phosphatase, aspartate aminotransferase, alanine aminotransferase, and lactate dehydrogenase. These samples will be collected for processing by the central laboratory. Samples must be collected before study treatment administration. Calculated Creatinine Clearance (CrCl) must be assessed during the screening period to determine eligibility. See the laboratory manual for more information.
- j. Urine dipstick testing will be performed locally at the site.
- k. Patients will provide any historical documentation of HLA type at the pretreatment screening visit. The majority of patients will not have such information available and must undergo HLA typing assessment at participating sites.
- l. ***For AML patients ONLY:*** provide historical documentation of cytogenetic and molecular analyses results (from initial diagnosis) at the pretreatment screening visit. Only patients with abnormal karyotype at initial diagnosis will require to repeat karyotype plus/minus fluorescence in situ hybridization (FISH) at pretreatment screening in this study. Full molecular analysis (i.e., FLT3-ITD and NPM1 mutations, etc.) will also be performed on bone marrow biopsy samples collected during pretreatment screening in all AML patients.
- m. ***For AML patients ONLY:*** a bone marrow aspiration and biopsy is required during pretreatment screening to confirm morphologic partial response (PR) or stable disease (SD) status, for MRD analysis, and for cytogenetic and molecular analyses as defined in footnote k. Additional bone marrow biopsies are required as shown per schedule, as well as at the end-of-treatment/early termination visit to evaluate progression and MRD. If a peripheral blood differential result (including manual differentiation) at any study visit is suggestive of abnormal or immature cells and a possible relapse, a bone marrow biopsy must be performed as part of a scheduled AML relapse visit. If the bone marrow biopsy confirms relapse, the patient will be discontinued from the study and will need to return to the site 0 to 30 days after their last treatment injection for end-of-treatment/early termination procedures. The bone marrow aspiration performed as part of the scheduled relapse visit will serve as bone marrow aspiration procedure required at the end-of-treatment/early

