6.1.5. Relapse Visit

In addition to the SOA above, one additional series of assessments will be performed at the time of tumor (or leukemia) relapse. Indeed, to assess PFS, it is important to document disease relapse. At the time of the “relapse visit”, the following assessments will be performed:

- Collect and update concomitant medication information
- Collect and update AEs
- Obtain ECOG performance score
- Obtain vital signs and document weight
- Collect blood samples for the central laboratory
 - Hematology (CBC with differential and platelet count)
 - Serum chemistry
 - Immune/exploratory correlates
- Evaluate clinical endpoints

For AML patients in specific, PB differentials from CBCs collected during every visit will be used to determine initially if the patient has relapsed, as defined by loss of CR status (if previously achieved) or further progression beyond initially achieved PR. For abnormal CBCs, a manual differential is required. If the differential is suggestive of abnormal or

immature cells and a possible relapse, a BM aspiration must be performed as part of a scheduled relapse visit to confirm the diagnosis of recurrent/relapse/refractory AML. A BM biopsy must be performed if an adequate aspiration is not attainable. In patients with AML who achieve CR status while on investigational therapy (galinpepimut-S plus pemrolizumab – administered on top of their continuing HMA regimen), relapse (post-CR) will be defined as a reappearance of leukemic blasts in the PB or >5% blasts in the BM not attributable to any other cause (e.g., BM regeneration after chemotherapy [[Cheson et al, 2003](#)]). If relapse is confirmed, the patient should be discontinued from the on-treatment portion of the study due to recurrent/refractory/relapsed AML and will need to return to the site 0 to 30 days after their last treatment injection for final safety follow-up and completion of the EOT/early termination visit procedures. The BM aspiration performed as part of the scheduled relapse visit will serve as BM aspiration procedure required at the EOT/early termination visit.

Once EOT/early termination visit procedures have been completed, the physician can choose to treat the documented recurrent/refractory/relapsed disease with any subsequent therapy they choose. The patient will be moved to the off- treatment follow-up period and will be followed only for AEs and OS.

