7.6.1. Analysis of Primary Efficacy Endpoint

For each tumor-specific cohort, a Bayesian approach with non-informative Jeffreys prior beta distribution with parameters $a = 0.5$ and $b = 0.5$ will be used to estimate the ORR and its 95% credible interval based on the posterior distribution.

At the time of analysis, within each tumor-specific cohort, the prior distribution will be updated with all available data to obtain the posterior distribution of the true ORR. The posterior probabilities that ORR exceeds TV and LRV will be reported for each cohort. A high posterior probability that $ORR > LRV$ will support a “Go” decision to continue development in the cohort, and a low posterior probability that $ORR > TV$ will support a “Stop” decision to halt development in the cohort. A “Consider” decision results if neither a Stop nor a Go decision can be made. The specific criteria for making a Stop, Consider, or Go decision within each tumor-specific cohort are derived using the following acceptable risks:

- 10% false stop risk: maximum acceptable probability that $ORR > TV$ given that a Stop decision is made.

- 20% false go risk: maximum acceptable probability that $ORR \leq LRV$ given that a Go decision is made

Before reaching the planned sample size in a cohort, the posterior probabilities will be updated continuously after each patient or group of patients and will be used to determine, within each cohort, the predictive probability of eventually reaching a Stop decision at the planned sample size. If this predictive probability is $\geq 80\%$, then enrollment in that cohort may be stopped early for futility. Definitions of the decision boundaries can be found in [Section 7.6.6](#).

In general, Stop/Go and futility decision criteria are non-binding and may be regarded as guidance and information to be integrated with a full medical review of safety and efficacy data observed at the time of analysis in determining the next course of action.

No tests of statistical significance are planned.

Patients with missing ORR will be conservatively classified as non-responders for the primary analysis.

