10.3.2. Protocol Deviations

A deviation from the protocol is an unintended or unanticipated departure from the procedures or processes approved by the sponsor and the IRB and agreed to by the investigator. A significant deviation occurs when there is nonadherence to the protocol by the patient or investigator that results in a significant, additional risk to the patient. Significant deviations can include nonadherence to inclusion or exclusion criteria, enrollment of the patient without prior sponsor approval, or nonadherence to regulatory authority regulations or ICH GCP guidelines and will lead to the patient being withdrawn from the study ([Section 4.2](#)).

There should be no deviations or departures from the protocol. The investigator may implement a deviation from, or a change of, the protocol to eliminate an immediate hazard to study patients without prior IRB approval. If an emergency occurs that requires departure from this protocol, the investigator or other physician in attendance in such an emergency will, if circumstances and time permit, contact the medical monitor. Such contacts will be made to permit a decision as to whether or not the patient will be continued on the study. As soon as possible after such an occurrence, the implemented deviation or change, the reasons for it, and any proposed protocol amendments should be submitted to the IRB for review and approval, to the sponsor for agreement (if not already done), and to the regulatory authorities, if required.

The site investigator or designee must clearly document and explain in the patient's source documentation any deviation from the approved protocol. Protocol deviations will also be documented by the clinical monitor throughout the course of monitoring visits. Principal investigators will be notified in writing by the monitor of deviations. The sponsor and IRB should be notified of all protocol deviations in a timely manner.

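### Section 10.3.2 and the repeated-DLT rule take patients out of the study, whereas Sections 4.2 and 4.2.1 and the full analysis set keep them in; leaving treatment and leaving the study need to be stated separately

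*Combined protocol and SAP*

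**What the plan says.** Three places use study-level wording.

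- **Section 10.3.2.** A significant deviation is nonadherence by patient or investigator that puts the patient at significant added risk. Examples are breaches of the entry criteria, enrolment without prior sponsor approval, and "nonadherence to regulatory authority regulations or ICH GCP guidelines and will lead to the patient being withdrawn from the study". The sentence ends by citing Section 4.2.
- **Sections 5.3.6.1 and 5.3.6.2, and the synopsis.** "If a DLT occurs after these dose modifications in subsequent cycles, the patient will be discontinued from the study". The bulleted summaries say the same of a third DLT.
- **Table 8, footnote m (AML).** "If the bone marrow biopsy confirms relapse, the patient will be discontinued from the study".

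Other places keep the patient in the study.

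- **Section 4.2.** All patients are followed for primary, secondary and exploratory endpoints unless they die or formally withdraw consent to survival follow-up.
- **Section 4.2.1.** "Discontinuation of study treatment does not represent withdrawal from the study". Patients may be removed from treatment, from on-treatment assessments, or "from off-treatment study assessments but continue to be monitored in the study for the following reasons". The reasons include "Patient was erroneously admitted into the study or does not meet entry criteria", a serious or intolerable AE, progression and noncompliance.
- **Section 6.1.5.** At confirmed AML relapse, "the patient should be discontinued from the on-treatment portion of the study", and follow-up continues for AEs and OS.
- **Sections 6.3 and 7.5.** PFS and OS are assessed in all patients on the ITT principle. The full analysis set includes patients with major deviations.

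Section 7.6.1 adds: "Patients with missing ORR will be conservatively classified as non-responders for the primary analysis".

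**The concern.** One event, such as an ineligible patient found after enrolment, has two opposite consequences depending on the section a site reads. Section 10.3.2 cites Section 4.2, but Section 4.2 does not say what 10.3.2 says.

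The label matters because Section 4.2.2 attaches different follow-up to it. A patient who stops treatment but remains on study continues the assessment schedule to the end of the study. For a patient who withdraws from the study, it specifies end-of-treatment procedures and a repeat four weeks after treatment stops.

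A site that applies the study-level wording literally could therefore stop collecting data on patients whom the full analysis set still counts. At stake are confirmation of a first response, and the later course of DOR, PFS, time to next treatment and OS in deviators and repeated-DLT patients. In the repeated-DLT group the reason for removal is toxicity, so censoring at removal may be informative. After AML relapse only OS and time to next treatment are exposed.

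**Working it through.** **Side-by-side reading**

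| Event | Study-level wording | Opposing text |
|---|---|---|
| Ineligible patient enrolled | 10.3.2: withdrawn from the study | 4.2.1: stays monitored; 7.5: stays in the full analysis set |
| Other significant deviation | 10.3.2: withdrawn from the study | 4.2: followed unless death or withdrawn consent; 4.2.1: noncompliant patients stay monitored |
| DLT after the schedule changes | 5.3.6.1, 5.3.6.2, synopsis: discontinued from the study | 4.2.1: AE patients stay monitored |
| AML relapse | Table 8 footnote m: discontinued from the study | 6.1.5: only the on-treatment part ends; 6.4.1.6: moved to off-treatment follow-up |

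The 10.3.2 sentence is ungrammatical. The consequence may attach to every listed deviation or only to the last one. Either reading conflicts with 4.2 and with the full analysis set.

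**Endpoints exposed under literal use**

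1. *ORR, solid tumors.* Section 6.8.2 requires confirmatory imaging at least four weeks after the first sign of response. A patient removed before that scan has no confirmed response and may be counted as a non-responder under 7.6.1. The denominator is unchanged, so the effect is downward.
2. *DOR, PFS, time to next treatment, OS.* Observation ends at removal for deviators and repeated-DLT patients.
3. *AML relapse.* Relapse is itself the PFS and DOR event, so only OS and time to next treatment could be cut off.

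**Illustration for ORR**

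Inputs: cohort sizes, boundaries and target values (TV) from Table 14. With X the number of responders, P(Go) = P(X ≥ g) and P(Stop) = P(X ≤ s), where X ~ Binomial(n, TV).

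Reproducing Tables 11–13 at TV:

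- CRC/OvC (n=20, g=4, s=1, 20%): Go 58.9%, Stop 6.9% (stated 59, 7).
- SCLC (n=20, g=8, s=5, 40%): Go 58.4%, Stop 12.6% (stated 58, 13).
- TNBC (n=15, g=4, s=1, 25%): Go 53.9%, Stop 8.0% (stated 54, 8).

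Now assume a fraction l of patients is removed before a response is recorded, independently of response, and counted as non-responders. The observable rate becomes TV × (1 − l). The documents give no value for l; 5% and 15% are assumptions.

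| Cohort | Rate at l = 5%, 15% | P(Go): 0 → 5%, 15% | P(Stop): 0 → 5%, 15% |
|---|---|---|---|
| CRC/OvC | 0.19, 0.17 | 58.9% → 54.4%, 45.0% | 6.9% → 8.4%, 12.3% |
| SCLC | 0.38, 0.34 | 58.4% → 51.1%, 36.2% | 12.6% → 16.7%, 27.6% |
| TNBC | 0.2375, 0.2125 | 53.9% → 49.3%, 39.9% | 8.0% → 9.7%, 14.0% |

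Losing one responder at the minimum Go count (4 to 3, or 8 to 7) moves a cohort to Consider. AML is left out because the confirmatory-scan mechanism concerns tumor imaging.

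**The case against.** The strongest case is that this is loose wording with little practical effect, and much of it stands.

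- Section 10.3.2 cites Section 4.2, which can be read as governing what withdrawal means. But the cited section never says that a deviation leads to withdrawal from the study. The cross-reference exposes the conflict without settling it.
- A reader might infer that any site error removes a patient. The documents do not support that: 10.3.2 is limited to deviations that bring significant added risk.
- A reader might infer that data on these patients would not exist. That goes too far. Section 6.1.4 and Table 8 footnote c send early discontinuers with at least one injection to off-treatment follow-up for PFS and OS. Section 6.8.3 asks for a scan at treatment discontinuation, then imaging every three months if there is no progression. Section 4.2.2's end-of-treatment procedures, repeated at four weeks, may also catch some confirmations.
- A reader might infer that safety data on repeated-DLT patients are lost. Section 4.2.2 calls for safety follow-up in every case. Section 6.4.1.7 follows AEs to resolution or stability and adds a later SAE call. Short-term safety is protected.
- Footnote m is the weakest example, since 6.1.5 and 6.4.1.6 correct it. Calling removal at relapse informative censoring of PFS or DOR would be wrong.
- The third-DLT rule applies only after two rounds of schedule change, often after response has been assessed, and the Go/Stop criteria are non-binding. The P(Go) figures therefore cannot be read as the effect of this wording.

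What remains is that a site following 10.3.2 or the DLT rule as written is told to take the patient off study, and 4.2.2 then gives that patient a shorter schedule.

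**Conclusion.** The contradiction is certain from the text: 10.3.2 and the repeated-DLT rule against 4.2, 4.2.1, 6.3 and the full analysis set. Footnote m is a lesser instance. The data loss is a risk that depends on sites applying the study-level wording literally.

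If it occurs, ORR is biased downward and follow-up for DOR, PFS, time to next treatment and OS is shortened in deviators and repeated-DLT patients. After AML relapse it affects only OS and time to next treatment.

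The size cannot be estimated from the documents. The illustrative fall in P(Go) in CRC/OvC, from 59% to 54–45%, rests on an assumed 5–15% loss that is independent of response and precedes any recorded response. The point should be corrected because later follow-up of these patients feeds analyses specified on the ITT principle.

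**What to change.** Reconcile 10.3.2, the DLT text (synopsis, 5.3.6.1, 5.3.6.2) and Table 8 footnote m with 4.2 and 4.2.1, so that leaving treatment and leaving the study are stated separately. Add that a patient affected by any of these rules stays in the study for response assessment (until progression or new anticancer therapy), safety, next-therapy and survival follow-up, unless consent is withdrawn. Use the 6.1.5 wording in footnote m.

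Section 10.3.2 makes removal mandatory, whereas 4.2.1 says patients may be removed. The sponsor must reconcile the two. No position is taken here on whether or when a deviation or a DLT must end treatment, and the follow-up statement should not alter those rules.

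The cost is a wording amendment. Off-treatment visits, three-monthly imaging and survival contacts are already planned for patients who stop treatment early (6.1.4, 6.8.3, Table 8 footnote c).

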10.4. Study Termination

Although SELLAS has every intention of completing the study, the sponsor reserves the right to close an investigational site or terminate the study at any time for clinical or administrative

reasons. In addition, the study may be stopped at a site at any time by the site investigator with appropriate notification.

10.5. First Interpretable Results (FIR) Report

A first interpretable results (FIR) report will be prepared. The exact data to be included in the FIR and its structure will be determined by the study master co-Principal Investigators, the data management/analysis and biostatistical teams (designees of SELLAS), the medical monitor(s), and the Chief Medical Officer and Head of Clinical Development of SELLAS

10.6. Final Complete Clinical Study Report (CSR)

Whether the study is completed or prematurely terminated, the investigator, where applicable, should inform the institution. The investigator/institution should provide the IRB with a summary of the study's outcome.

SELLAS Life Sciences Group will ensure that both interim, as well as final complete clinical study reports are prepared (as applicable) and provided to the regulatory agency(ies) as required by the applicable regulatory requirement(s). The sponsor will also ensure that the clinical study reports in marketing applications meet the standards of the ICH harmonised tripartite guideline E3: Structure and content of clinical study reports.

Where required by applicable regulatory requirements, an investigator signatory will be identified for the approval of the clinical study report. The investigator will be provided reasonable access to statistical tables, figures, and relevant reports and will have the opportunity to review the complete study results.

Upon completion of the clinical study report, the sponsor will provide the investigator with the full summary of the study results. The investigator is encouraged to share the summary results with the study patients, as appropriate. The study results will be posted on publicly available clinical trial registers.

11. Reference List

